In-/ exclusion criteria ⁴		X	X							
Physical examination		X	X			X			X ³	X ⁵
Laboratory tests		X							X ³	X ⁵
12-lead ECG		X	X			X			X ³	X ⁵
Pregnancy test ⁶		X							X ³	X ⁵
Training in use of RESPIMAT ⁷		X	X							
Dispense and explain use of rescue medication ⁸	X	X	X			X				
Collect rescue medication/accountability check ⁸		X	X			X			X ³	
Medication washout check		X	X			X			X	
Administration (dosing) of trial medication at the site			X			X ¹⁸			X ¹⁸	
██████████			X			X			X	
mMRC ²⁰		X								
Pulmonary Function Testing (PFT); FEV ₁ /FVC and SVC/IC)		X ⁹	X ¹⁰			X ¹¹			X ^{3,11}	
Vital signs (seated) ¹²		X	X			X			X ³	X ⁵
6MWT		X ²¹	X			X			X	
██████████		X ²¹	X			X			X	

Trial Periods	Screening Period		Treatment period 1				Treatment period 2			Trial Follow-Up	
	0 ¹	1	2	3	4	5	6	7	8		9
Visit Number	0 ¹	1	2	3	4	5	6	7	8	9	10
Week of treatment		-2	0	1	2	3	4	5	6	7	8
Day of treatment		-14	1	15	29	43	57	71	85	99	113
Visit window (days)		-7	N/A	-3	±1	+3	-3	±1	+3		+7
Physical activity monitoring ¹⁴		X	X	X	X	X	X	X	X	X	X
██████████			X			X			X		
██████████			X			X			X		
Patient Diary ²³		X	X			X			X ³		
██████████			X			X			X		
Muscle amount (% in BW)		X									
Telephone contacts ¹⁷				X	X		X	X			
Patient registration (IRT)		X									
Randomisation (via IRT)			X								
Dispense double-blinded trial medication			X			X					
Collect double-blinded trial medication and accountability check						X			X ³		
Adverse events		X	X	X	X	X	X	X	X ³	X	
Concomitant therapy		X	X	X	X	X	X	X	X ³	X	

EOT: End of Treatment, IRT: Interactive Response Technology, PFT: Pulmonary Function Testing, ██████████

██████████ mMRC: modified Medical Research Council, ██████████

██████████, 6MWT: 6 minute walk test

- ¹ Visit 1 may be scheduled 1-28 days after Visit 0 (depending on medication washout requirement as described in [Section 4.2.2.1](#). Patients who are treated with LABA and LAMA should be treated at least 3 weeks with one of its' component, i.e. LABA or LAMA.).
- ² All patients must sign an informed consent consistent with ICH-GCP guidelines and Japanese GCP regulations prior to participation in the trial, which includes medication washout and restrictions.
- ³ EOT examinations are completed by all patients who took at least one dose of trial medication and who discontinue early. Pulmonary Function Testing (PFT) is to be performed if possible.

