5.3.3 Safety laboratory parameters

Laboratory tests

Safety laboratory testing will be conducted (non-fasting) on all patients at the screening visit (Visit 1), and at Visit 4/EOT. Follow-up clinical laboratory testing will be performed at Visit 5 if there are any clinically significant findings at Visit 4/EOT. The laboratory tests at Visit 1 will be considered as the baseline measurements. Laboratory specimens will be collected in the morning prior to the exercise testing. Patients should be instructed not to do any unaccustomed physical exercise 36 hours prior to laboratory testing.

Haematology, blood chemistry, urinalysis will be analysed by the local laboratory.

Haematology

Haemoglobin, haematocrit, red blood cell count, white blood cell count including differential (neutrophils, lymphocytes, monocytes, eosinophils, basophils), total eosinophil count and platelet count.

Blood chemistry

Alkaline phosphatase, LDH, Gamma- glutamyl transferase (GT), aspartate aminotransaminase AST (SGOT), alanine aminotransaminase ALT (SGPT), glucose, calcium, inorganic phosphorus, uric acid, urea nitrogen, creatinine, total protein, potassium, sodium, chloride, total bilirubin, creatine kinase.

Urinalysis

Specific gravity, pH, glucose, protein, occult blood.

Pregnancy Testing

Pregnancy tests to be performed at Visit 1 and Visit 4/EOT. If a patient discontinues early, a pregnancy test will also be conducted.

Local laboratory will be used and the laboratory data will not be collected or captured in the eCRF. All laboratory values will be evaluated, (signed, dated and commented upon) by the investigator and stored locally. Any clinically relevant changes in the laboratory values will be reported as AEs (see [Section 5.3.6](#)) and followed up and/or treated locally until returning to normal or stable condition.

Any laboratory abnormalities will be carefully monitored and if necessary the patient will be removed from the trial and medically treated.

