6.2.2 Treatment periods

Clinic visits after 6 weeks of each treatment period (Visits 3 and 4):

Telephone Visit

The investigator or a designated site staff member will telephone the patients 15 days and 8 days prior to the next planned Visit and remind them to wear physical activity monitor every day. An assessment of adverse events including concomitant therapy should be performed from the last assessment. The investigator should ask the patient to visit the clinic, if determined by the investigator as concerning the patient's safety.

Observations / procedures:

Patients will be contacted prior to each of the visits to remind the patient of medication washout times, exercise test restrictions and to bring back all study medication at their next visit.

- Medication washout compliance will be verified at every visit as described in [Section 4.2](#).
- [REDACTED]
- Patient's smoking status will be recorded only at Visit 4/EOT.
- All adverse events experienced since the last visit will be reviewed and recorded.
- Any change of concomitant therapy since the last visit will be reviewed and recorded.
- A complete physical examination including vital signs (blood pressure and pulse rate) and 12-lead ECG will be conducted. The vital signs and ECG should be conducted following 5 minutes rest and prior to blood sampling.
- Blood and urine samples will be collected (only Visit 4/EOT). A pregnancy test will be performed for women of child-bearing potential.
- Study medication will be self-administered within \pm 30 minutes of time of administration next day of Visit 2 and between 7:00 a.m. and 10:00 a.m.; start-time of inhalation will be recorded. Administration of trial medication during these visits will be done using medication that was dispensed at the beginning of the treatment period.
- PFT should be performed as mentioned in [Flow chart](#) and respective protocol sections.
- 6MWT should be performed as mentioned in Flow chart and respective protocol sections.

- 
- All trial medications should be collected at Visit 3 and Visit 4/EOT. At Visit 3, new trial medications for the patients should be dispensed via IRT.

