6. GENERAL ANALYSIS DEFINITIONS

6.1 TREATMENTS

The doses to be administered are described in Section 4 of the CTP.

This is a crossover trial consisting of a two-week screening period followed by two six-week treatment periods and a three-week post-treatment period. The day after the follow-up visit will be considered the start of the post-study period in case there are any subsequent AE data we become aware of. In this study, there will be no washout between treatment periods.

For the main safety analysis, data occurring during the treatment periods and within 21 days of stop of study drug for that period will be assigned to the respective treatment for that period. Data occurring before the first drug intake date is assigned to "screening". If the next treatment period starts within 21 days of the end of the last period, data after the start of treatment for the next period will be assigned to the treatment for that period. In this trial, next treatment will be started after end of treatment of first period as soon as possible because there is no washout period as planned. Data more than 21 days after drug stop date for a period but before the start of the next period will be assigned to washout. Data more than 21 days after the end of the last treatment period and up to and including the date of the study termination will be assigned to post-treatment. Data after study termination will be assigned to post-study.

Any cases of patient being treated with the wrong study medication will be identified and summarised as an important protocol violation (PV).

- If a patient was treated with a treatment sequence different from the randomised treatment sequence throughout the on-treatment period, i.e., a patient was treated with incorrect study medication during every treatment period, this patient will be included in the treated set and will be analysed as treated for both efficacy and safety analyses, including patient disposition. Such a case will be reported as an important PV and this patient will be excluded from the per-protocol set (PPS).

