7. PLANNED ANALYSIS

For End-Of-Text tables, the set of summary statistics is: N / Mean / Standard deviation (SD) / Min / Median / Max.

Tabulations of frequencies for categorical data will include all possible categories and will display the number of observations in a category as well as the percentage (%) relative to the respective treatment group (unless otherwise specified, all patients in the respective patient set whether they have non-missing values or not). Percentages will be rounded to one decimal place. The category missing will be displayed only if there are actually missing values.

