The frequency of patients with AEs will be summarised by treatment, primary SOC and PT. Separate tables will be provided for patients with other significant adverse s according to ICH E3 (4), for patients with AEs leading to treatment discontinuation, for patients with AEs leading to death, for patients with investigator determined drug-related adverse events, and for patients with SAEs.

According to ICH E3 (4), AEs classified as 'other significant' include those non-serious and non-significant adverse events with

- (i) 'action taken = discontinuation' or 'action taken = reduced', or
- (ii) marked haematological and other lab abnormalities or that lead to significant concomitant therapy as identified by the Clinical Monitor/Investigator and confirmed at a BRPM.

The system organ classes will be sorted according to the standard sort order specified by the European Medicines Agency, PTs will be sorted by frequency (within SOC).

Standard AE analyses requested for public disclosure at CT.gov and European Union Drug Regulating Authorities Clinical Trials will also be provided in Section 16.1.9.2 of the CTR.

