7.8.2 Laboratory data

Clinically significant findings in laboratory data will be reported as "baseline conditions" or "adverse events" and will be analysed accordingly.

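### Completers have no scheduled laboratory test at the end of period 1, so by-drug tables of laboratory-detected AEs pull the difference between drugs towards zero

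*SAP*

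**What the plan says.** Protocol 5.3.3 sets the schedule: "Safety laboratory testing will be conducted (non-fasting) on all patients at the screening visit (Visit 1), and at Visit 4/EOT". It also fixes the reference point: "The laboratory tests at Visit 1 will be considered as the baseline measurements". Protocol 6.2.2 limits blood and urine sampling in the treatment periods to the last visit. The flow chart repeats physical examination, ECG and vital signs at Visit 3, but not laboratory tests. Its footnote 3 adds a test for those who stop early: "EOT examinations are completed by all patients who took at least one dose of trial medication and who discontinue early".

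Laboratory values are kept at the site and do not enter the eCRF (Protocol 5.3.3). Findings reach the analysis only by the route in SAP 7.8.2: "Clinically significant findings in laboratory data will be reported as 'baseline conditions' or 'adverse events' and will be analysed accordingly". SAP 5.4 accordingly counts clinically relevant laboratory changes within the AE variable.

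There is no washout, and SAP 6.1 attributes events by date: "data after the start of treatment for the next period will be assigned to the treatment for that period". SAP 7.8.1 states the output: "The frequency of patients with AEs will be summarised by treatment, primary SOC and PT". Safety analyses use the treated set (SAP 7.8). The percentage base in SAP 7 is the treatment group: "unless otherwise specified, all patients in the respective patient set whether they have non-missing values or not".

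**The concern.** In a two-period crossover each patient contributes to both drugs' AE denominators. For laboratory findings, a completer has a scheduled chance of detection on only one of the two drugs. A transient abnormality on the period-1 drug is likely to be missed. One that lasts until Visit 4 is found then and, if dated then, is counted for the other drug. Randomisation to sequence makes this symmetrical when the drugs are alike. It does not protect the comparison when they differ, because both mechanisms reduce the contrast.

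Protocol 7.3.3 gives comparison of AE incidence across treatments as a purpose of the tables. SAP 7.8.1 also provides a separate table of other significant AEs, for which marked laboratory abnormalities are one criterion. A reader could take similar percentages as evidence of similar laboratory safety when part of the similarity comes from the sampling schedule. Since no laboratory values are in the database, this cannot be repaired later from the data.

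**Working it through.** **Inputs from the documents.** 180 patients, 90 per sequence (Protocol 3.3); scheduled laboratory tests at Visit 1 and Visit 4/EOT; attribution by date, no washout; denominator all patients treated with the drug. The documents give no laboratory-AE rate, so there is no stated figure on this point to reproduce. The planned 180 itself reproduces: an exact one-sample t calculation with 0.1 L, SD 0.41 L and two-sided 0.05 needs 179 for 90% power and gives 90.2% at 180. The present point does not touch that calculation.

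**Step 1, coverage.** With no drop-out, the patients with a scheduled test on a given drug are those who take it second: 90/180 = 50%. If a share d drops out in period 1 and has the EOT test, coverage is 1/(2 − d): 51.3%, 52.6% and 55.6% for d = 5%, 10% and 20%. If drop-outs miss that test, it is (1 − d)/(2 − d): 48.7%, 47.4% and 44.4%. The values of d are assumptions.

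**Step 2, reported rates.** Let f and t be the 6-week rates that a test at the end of each period would find on the combination and on tiotropium. Let ρ be the share of period-1 abnormalities still present at Visit 4. Assume scheduled tests only, no drop-out, and onset dated at the sample. Then

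- reported combination rate = 90(f + ρt)/180 = (f + ρt)/2
- reported tiotropium rate = 90(t + ρf)/180 = (t + ρf)/2
- reported difference = (f − t)(1 − ρ)/2

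With assumed f = 6% and t = 3% (true difference 3.0 points):

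| ρ | Combination | Tiotropium | Difference (points) | Share of true difference |
|---|---|---|---|---|
| 0 | 3.0% | 1.5% | 1.5 | 0.50 |
| 0.5 | 3.75% | 3.0% | 0.75 | 0.25 |
| 1 | 4.5% | 4.5% | 0 | 0 |

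Allowing for patients with an abnormality in both periods changes little (4.41% instead of 4.5% at ρ = 1).

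**Step 3, single rates.** The ratio of reported to true rate for drug X against drug Y is ½(1 + ρ·pY/pX), which is never below one half. In the example the combination loses 50%, 37.5% and 25% at ρ = 0, 0.5 and 1. Tiotropium loses 50%, then nothing, then is overstated by 50%.

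**Step 4, tests outside the schedule.** If a share u of period-1 findings is picked up in period 1 and correctly attributed, the retained share of the difference is ½[(1 + u) − (1 − u)ρ]. At ρ = 0 this is 0.55 for u = 0.1 and 0.625 for u = 0.25. At u = 0.25 and ρ = 0.5 it is 0.44.

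**Step 5, tabulation by sequence.** Over the 90 patients of each sequence, the percentages with a Visit 4 finding are f + ρt (combination last) and t + ρf (tiotropium last). Their difference is (f − t)(1 − ρ), twice what the by-drug table retains. In the example: 6.0% against 3.0% at ρ = 0, 7.5% against 6.0% at ρ = 0.5, and 9.0% against 9.0% at ρ = 1.

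**The case against.** A reader might infer that each drug's laboratory-AE rate is understated by half or more. The documents do not support that. Step 3 shows that half is about the largest loss for a rate, reached when every period-1 abnormality resolves before Visit 4 and none is found otherwise. It is exceeded slightly only if drop-outs miss their EOT test. With persistence the loss is smaller and the lower-rate drug may be reported too high. A change arising between the Visit 1 baseline and first dose can also appear at Visit 4 and be counted for the period-2 drug.

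Loss of half or more is not certain for the difference either. Early discontinuers have EOT tests. Protocol 5.3.6.1 calls for unscheduled blood tests when symptoms suggest hepatic injury. Telephone contacts can lead to a clinic visit. Dating onset at the sample is also an assumption, since the investigator records onset. It is a natural one for a symptomless change with no earlier sample, but the plan does not state it.

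A laboratory-AE rate by drug is not a named endpoint, the AE denominator is the ordinary one, and Protocol 7.3.3 plans no hypothesis tests for safety. All this stands and limits the weight of the point.

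The tabulation by sequence has its own weakness. At ρ = 0.5 it shows 7.5% and 6.0% against true rates of 6% and 3%, so read as per-drug rates it would overstate both. That settles how the table must be labelled. It is not a reason to omit it, because it retains twice the contrast. The episode-collapsing rule in SAP 7.8.1 does not help, as it needs an occurrence already recorded in period 1.

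**Conclusion.** The point holds as a limitation of the descriptive safety tables that the SAP should address. For completers, about half of each drug's treated patients (about 90 of 180) have no scheduled laboratory test on that drug, yet all of them stay in the denominator, and a persisting period-1 finding may be counted for the wrong drug. With scheduled tests only, no drop-out and onset dated at the sample, the between-drug difference keeps (1 − ρ)/2 of its true size: about half if findings are transient, none if all persist. Tests outside the schedule soften this by an amount the documents do not allow one to estimate. The 6% and 3% rates and the values of ρ, u and d are illustrative. The claim does not extend to a loss of half or more in every drug's rate, nor to the primary analysis, the secondary analyses or the sample size.

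**What to change.** In SAP 7.8.1 and 7.8.2:

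- Keep the standard by-treatment AE table.
- At the blinded report planning meeting, identify the AEs first detected in the scheduled Visit 4 laboratory sample. SAP 7.8.1 already has laboratory-abnormality AEs confirmed at such a meeting.
- Add one descriptive table of these AEs by treatment sequence, with patients who attended the scheduled Visit 4 in that sequence as denominator. List findings from early-EOT samples in period 1 under the period-1 drug.
- Title it *laboratory AEs detected at Visit 4 by sequence*, not as a per-drug 6-week rate. Footnote that period 1 had no scheduled laboratory test for completers and that onset on the earlier drug cannot be excluded.

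The cost is SAP wording, one table and a manual blinded flag. The flag will need AE dates or site queries, because laboratory values are not in the eCRF. The table rests on about 90 patients per group, conditions on reaching Visit 4, and gives up the within-patient comparison. It corrects the denominator but cannot recover the attribution of persisting findings.

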7.8.3 Vital signs

Only descriptive statistics are planned for this section of the report.

7.8.4 ECG

Clinically significant findings in ECG data will be reported as "baseline conditions" or "adverse events" and will be analysed accordingly.

7.8.5 Others

This section is not applicable.

9. ADDITIONAL SECTIONS

PROGRAMMING CODE FOR INFERENCE ANALYSIS

- SAS codes for primary analysis:

```
PROC MIXED data=indata order=internal method=reml cl covtest;  
  CLASS trtgrp period usubjid;  
  MODEL ept = trtgrp period eptbase / ddfm=kr solution;  
  repeated period / type=cs subject=usubjid r rcorr;  
  LSMEANS trtgrp / pdiff cl;  
RUN;
```

The endpoint is denoted by `ept`, `eptbase` denotes the baseline value of the endpoint, `trtgrp` denotes treatment, `period` denotes the treatment period, and `usubjid` denotes patient number.

10. HISTORY TABLE

Table 10: 1 History table

Version	Date (DD-MMM-YY)	Author	Sections changed	Brief description of change
Final	10-APR-2017	██████ ██████	None	This is the final TSAP without any modification.
